4.1 ANALYSIS POPULATIONS

4.1.1 Safety Population

All patients who are enrolled and received any dose of RO7234292, whether prematurely withdrawn from the study or not, will be included in the safety analyses.

The Safety Population will be the primary population for all safety analyses and patients will be analyzed by dose received.

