For all other lumbar punctures, CSF fluid (20 mL) will be collected by needle using a lumbar puncture collection kit. If there are difficulties in collecting 20 mL of CSF fluid, a minimum of 5 mL should be collected over a maximum of 60 minutes. The operator must confirm CSF flow is present prior to any injection of study drug. A 24G (atraumatic) needle should be used to minimize risk of post-lumbar puncture syndrome. Depending on institutional guidelines, local anesthesia should be used for the procedure. Sedation may not be used. Spinal ultrasound may be used for the lumbar puncture procedure if deemed necessary, but ultrasound is not required. Ultrasound guidance may be used if attempts at lumbar puncture without imaging are unsuccessful, if it is local practice to use ultrasound, or if institutional guidelines dictate use of ultrasound with each lumbar puncture. For details on the lumbar puncture and IT bolus dosing procedure, please refer to the lumbar puncture manual and instructional video.

Lumbar punctures will be performed as specified in [Appendix 1](#) and [Appendix 2](#).

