4.6.2 Patient Discontinuation from Study

Patients have the right to voluntarily withdraw from the study at any time for any reason. In addition, the Investigator has the right to withdraw a patient from the study at any time. Reasons for withdrawal from the study may include, but are not limited to, the following:

- Patient withdrawal of consent
- Study termination or site closure

Every effort should be made to obtain information on patients who withdraw from the study but have not withdrawn consent. The primary reason for withdrawal from the study should be documented on the appropriate eCRF. If a patient requests to be withdrawn from the study, this request must be documented in the source documents and signed by the Investigator. Patients who withdraw from the study will not be replaced.

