5.1.1.4 Known Risks Associated with an Indwelling Catheter

Insertion of an intrathecal catheter carries the same risks as a lumbar puncture, with additional risks of catheter blockage, disconnection or retraction.

Of note, in the current study, 2 out of 6 patients developed a lumbar abscess after having had the catheter implanted for 4 days.

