6.3 ANALYSIS POPULATIONS

6.3.1 Safety Analysis Population

All patients who have received at least 1 dose of the study drug, whether prematurely withdrawn from the study or not, will be included in the safety analyses.

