6.4 SAFETY ANALYSES

All safety analyses will be based on the safety analysis population. The safety data, including adverse events, reasons for withdrawal from study, laboratory data, ECG, concomitant medications, vital signs, physical and neurological examinations, and C-SSRS, will be reported in individual listings and summarized by treatment for each assessment time using descriptive statistics.

The incidence of adverse events will be summarized on the basis of body systems and Medical Dictionary for Regulatory Affairs preferred terms. The incidence of adverse events by severity and relationship to study drug or study procedure and incidence of marked abnormal laboratory test results will be provided.

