4.7.2 Adverse Events

All treatment-emergent adverse events (TEAEs) and serious adverse events (SAEs) will be summarized for each dose level and for all patients using the Medical Dictionary for Regulatory Activities (MedDRA) coding by system organ class, preferred term, relationship to Study Drug, and severity. Missing data will be handled as described in Section 4.6. Percentages presented in AE tables will display the percentage of patients within a treatment dose level experiencing the AE at least once.

For frequency counts by preferred term, multiple occurrences of the same AE in an individual are counted only once. For overall total number of events, multiple occurrences of the same AE in an individual are counted separately.

An adverse event will be regarded as treatment emergent adverse event (TEAE) if the event occurs after the first dose of treatment or worsened after treatment.

Adverse events that occur before first dose administration and are not related to study procedure will be included in data listings only. SAEs and non-serious AEs that lead to treatment discontinuation or treatment interruption will be listed separately. Selected AEs, for instance procedure related AEs, will be summarized and listed separately.

Additional analyses will be considered to describe the impact of COVID-19 on patient safety.

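### A patient with an attempted catheter insertion who is therefore never dosed has no place in the planned procedure-related adverse-event summaries

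*SAP*

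**What the plan says.** SAP 4.1.1 defines the Safety Population as "All patients who are enrolled and received any dose of RO7234292, whether prematurely withdrawn from the study or not". It continues: "The Safety Population will be the primary population for all safety analyses and patients will be analyzed by dose received". Protocol 6.3.1 uses the same criterion ("All patients who have received at least 1 dose of the study drug"), and protocol 6.4 states: "All safety analyses will be based on the safety analysis population". Neither document defines a set of enrolled or catheterised patients for safety purposes.

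Procedural events are nevertheless meant to be reported. Protocol 6.4 plans adverse-event incidence by relationship to the study procedure as well as to the drug. SAP 4.7.2 says: "Selected AEs, for instance procedure related AEs, will be summarized and listed separately". The same section confines pre-dose events to listings only if they are unrelated to a study procedure, and takes percentages in adverse-event tables within dose level.

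On the order of events, protocol 1.3 puts catheter insertion and baseline CSF sampling ahead of the first dose on Day 1, and protocol 4.3.2 gives that dose through the catheter. Protocol 4.5.5 adds: "The operator must confirm CSF flow is present prior to any injection of study drug". On risk, protocol 5.1.1.4 says: "Insertion of an intrathecal catheter carries the same risks as a lumbar puncture, with additional risks of catheter blockage, disconnection or retraction". Protocol 4.6.2 says: "Patients who withdraw from the study will not be replaced".

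**The concern.** Exposure to the procedure begins at insertion, while membership of the analysis set begins at the dose. If the insertion fails, or causes a complication that prevents dosing, the patient has met the procedural hazard but is not in the set used to measure it. Exclusion then depends on how the procedure went, which is what the table is meant to describe.

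This also sets SAP 4.7.2 against SAP 4.1.1. The first implies that pre-dose procedure-related events belong in the tables. The second leaves no row or column for such an event in a patient who never received RO7234292.

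Procedural harm is a live issue in this study. Protocol 5.1.1.4 reports lumbar abscess in 2 of 6 patients, and Version 4 shortened the catheter period and added infection precautions. With four patients planned per dose level, one omitted patient visibly changes a table.

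**Working it through.** The documents state no figure on this point, and protocol 6.1 disclaims a formal basis for the sample size, so there is no sponsor calculation to reproduce. The check is a reading of the rules followed by illustrations.

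**1. Who is lost.** Three Day 1 courses, under the rules as written:

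| Course | In Safety Population? | Event can be tabulated? |
|---|---|---|
| Insertion uneventful, dosed | Yes | Not applicable |
| Harmed at insertion, then dosed | Yes | Yes; SAP 4.7.2 does not confine it to listings |
| Insertion attempted, never dosed | No | No; no dose received, so no group |

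Only the third course falls through.

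**2. Size if it happens once.** Inputs: 4 patients per dose level and 12 planned (protocol 3.1, SAP 2). I assume that one catheterised patient is never dosed and that the no-replacement rule in protocol 4.6.2 applies to that patient. Brackets give exact (Clopper-Pearson) 95% intervals.

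| Assumed case | As planned | All attempted insertions counted |
|---|---|---|
| Undosed patient has the only event, dose group | 0/3 = 0% (0 to 70.8) | 1/4 = 25.0% (0.6 to 80.6) |
| Undosed patient has the only event, 12 patients | 0/11 = 0% (0 to 28.5) | 1/12 = 8.3% (0.2 to 38.5) |
| Undosed patient has an event, two others do too | 2/11 = 18.2% (2.3 to 51.8) | 3/12 = 25.0% (5.5 to 57.2) |
| Undosed patient has no event, two others do | 2/11 = 18.2% (2.3 to 51.8) | 2/12 = 16.7% (2.1 to 48.4) |

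The first three rows understate the incidence and the fourth slightly overstates it. The intervals overlap heavily in every row. What is at stake is whether an event appears in the table at all, not the precision of a rate.

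**3. Chance that it arises.** The documents give no rate of non-dosing after attempted insertion. Let p be that per-patient rate, assumed to lie between 2% and 10%. The chance of at least one such patient among n is 1 − (1 − p)^n.

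| n | p = 2% | p = 10% |
|---|---|---|
| 12 (all planned) | 1 − 0.98^12 = 22% | 1 − 0.90^12 = 72% |
| 6 (12 − 6 already catheterised) | 1 − 0.98^6 = 11% | 1 − 0.90^6 = 47% |

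The second row assumes that all six patients mentioned in protocol 5.1.1.4 were dosed. Both rows give the chance of any undosed patient, with or without an event, so they are not the chance of an understated rate.

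**The case against.** The strongest reply is that the gap is narrow and may never open. Much of that stands.

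- A reader might infer that any patient harmed before the first dose is lost. That is not so: a patient harmed at insertion and then dosed stays in the Safety Population.
- A reader might infer that the procedure-related rate is always biased low. The direction depends on the undosed patient: an event-free failed insertion pushes the rate the other way.
- A reader might take the two abscesses as cases that this rule would hide. The protocol says that they followed four days of catheter implantation, and nothing suggests that those patients were undosed. They show that catheter harm matters here, but they are not a pre-dose rate.
- A reader might say that the study exists to show whether the 48-hour catheter is tolerable. The primary objectives are PK, the mHTT time course and PK/PD, and the secondary safety objective concerns two intrathecal doses of RO7234292.
- The event is not erased. Protocol 5.3.1 has it recorded on the eCRF, and the patient still counts in the disposition summaries of SAP 4.3 and protocol 6.2.

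It can also be argued that the SAP calls the Safety Population primary, not exclusive, and declares that it supersedes the protocol. That leaves room for another set, but the SAP names none, and grouping by dose received still gives an undosed patient no column. The protocol did foresee untreated patients elsewhere: section 6.6 groups them by assigned treatment for immunogenicity. Procedural events have no matching rule.

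**Conclusion.** The point holds for one kind of patient: insertion attempted and, for that reason, no dose given. Such a patient is missing from numerator and denominator of the procedure-related summaries, contrary to what SAP 4.7.2 implies. If that patient had the only event, 1/4 becomes 0/3, or 1/12 becomes 0/11. If that patient had none, the rate rises slightly. If every catheterised patient is dosed, the effect is zero.

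How likely this is rests wholly on the assumed 2% to 10% rate, and on whether 12 or only six patients are still at risk. No primary endpoint or formal test is touched. This is an inexpensive improvement that closes a conflict between two sections of the SAP. It does not show that any result is wrong.

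**What to change.** - Keep the Safety Population for drug-related and treatment-emergent summaries.
- In SAP 4.1, add a Procedure Safety Population: all enrolled patients in whom intrathecal catheter insertion or a study lumbar puncture was attempted, whether or not RO7234292 was given.
- In SAP 4.7.2, base the procedure-related adverse-event and serious adverse-event summaries on it, showing undosed patients under their assigned dose level and in the total column. Appendix 1 schedules treatment assignment ahead of catheter insertion, so an assigned level should exist.
- In protocol 6.4, exempt these tables from the rule that all safety analyses use the dosed population.
- Reconcile protocol 5.3.1, which has all pre-dose events caused by a protocol procedure reported, with Appendix 1 footnote dd, which asks only for serious ones. Until they agree, non-serious events may be missing from the numerator.

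The cost is a few sentences in each document and one population flag. No new data are needed if the 5.3.1 rule is the one in force. The small downside is that the procedure table may have a different denominator from the drug-related table, which a footnote can explain.

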4.1.2 Immunogenicity Population

All patients who received any dose of RO7234292 and with at least one post-dose ADA assessment.

4.1.3 Pharmacokinetic Population

All patients who are enrolled and receive at least 1 dose of RO7234292, have not significantly deviated from the protocol, violated inclusion or exclusion criteria. Patients with incomplete data may be excluded if this would undermine the interpretability of the PK analysis. Excluded cases will be documented together with the reason for exclusion.

4.1.4 Pharmacodynamic Population

All patients who are enrolled and receive at least 1 dose of RO7234292, have not significantly deviated from the protocol, violated inclusion or exclusion criteria. Patients with incomplete data may be excluded if this would undermine the interpretability of the PD analysis. Excluded cases will be documented together with the reason for exclusion.

4.2 **BASELINE DEFINITIONS**

For all assessments, baseline will be defined as the last non-missing measure prior to the first dose administration. For fluid biomarkers, if appropriate time-matched baseline may also be considered to assess diurnal effects.

4.3 **ANALYSIS OF STUDY CONDUCT**

The number of patients who enroll in the study, discontinue from the study, and complete the study will be summarized overall and by dose level. Reasons for premature study withdrawal will be listed and summarized. All major protocol deviations will be listed and summarized.

Additional analyses will be performed to assess and describe the impact of COVID-19 on the study conduct.

4.4 **ANALYSIS OF TREATMENT GROUP COMPARABILITY**

Demographic and baseline characteristics will be summarized by dose level using but not limited to n, mean, standard deviation, median and range for continuous variables and proportion for categorical variables, as appropriate. Summaries will be presented overall and by dose level.

4.5 **DATA HANDLING RULES**

For safety laboratory and measurements that are reported as ' $<x$ ' or ' $>x$ ', the analysis value will be replaced by 'x'. For biomarkers (e.g. CSF mHtt, CSF NfL, etc) where entries will be indicated as 'BLQ', the analysis value will be set to BLQ divided by 2 (BLQ*0.5). No imputation will be performed on missing entries without a corresponding BLQ limit. In case of listing, however, the original data entries will be presented.

A summary table for subjects with imputed values by dose level and visit will be presented for each parameter.

For CSF/plasma biomarkers (e.g. NfL, mHtt) and CSF protein, scatter plots to assess relationships will be based on the natural log-transformed parameter.

For PK concentrations, BLQ values will be set to zero if corresponding time was prior to Tmax and set to missing after Tmax.

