2.1.1 Primary Endpoints

The corresponding primary endpoints are as follows:

- CSF and plasma concentrations of RO7234292
- Change from baseline of mHTT concentrations in CSF
- Relationship between plasma and/or CSF concentration or PK parameters and biomarker measures (mHTT in CSF)

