3.3 RATIONALE FOR STUDY DESIGN

3.3.1 Rationale for RO7234292 Dose and Schedule

In order to characterize the concentration time profile of RO7234292 and mHTT in plasma and CSF and the influence of dose on the magnitude and duration of mHTT lowering in CSF, initially, two IT bolus doses ranging from 30 mg up to 120 mg given 28 days apart will be investigated in the present study. Data from the completed Phase I/Ia multiple ascending dose (MAD) study (ISIS 443139-CS1) showed doses up to 120 mg IT RO7234292 over four doses administered every 28 days were safe and well tolerated. Dose-dependent reductions of CSF mHTT from baseline at the end of the dosing interval after IT administration of doses ranging from 10 mg to 120 mg were observed.

In the chronic toxicology study in monkeys, the No Observed Adverse Effect Level was determined to be 35 mg dose. Conservatively correcting for differences in CSF volume between monkeys (\leq 15 mL) and humans (\geq 150 mL) with a scaling factor of 10, the human equivalent dose corresponds to 350 mg, representing a 3-fold safety margin to the proposed maximum dose of 120 mg, to be evaluated in the present study.

Further details on non-clinical and clinical studies can be found in the Roche Investigator's Brochure.

The target reduction for clinical efficacy based on a non-clinical PK/PD model is at least 30% reduction in CSF mHTT. The administration of two IT doses of RO7234292 lead to trough percentage change of CSF mHTT of -25%, -28%, and -30% on average for 60 mg, 90 mg, and 120 mg of RO7234292 in the Phase I/Ia MAD study (ISIS 443139-CS1).

Using a model developed based on data from the completed Phase I/IIa study *and the ongoing OLE Study BN40697*, non-linear mixed-effects simulations predict *two* IT doses of 30 mg, 60 mg, 90 mg, and 120 mg of RO7234292 are to result in *median* percentage change from baseline of CSF mHTT of -24%, -27%, -29%, and -30%, respectively, *at the end of the dosing interval (29 days) after the second IT administration*. Therefore, in order to characterize a mHTT concentration-time curve in the relevant range of mHTT reduction (~30% reduction), two IT doses administered every 4 weeks will be studied in this study.

Once a clear concentration effect has been established (peak effect and time course of effect) the information may inform a different dose regimen, including the potential for less frequent dosing.

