4.3.2 Study Treatment Dosage, Administration, and Compliance

The treatment regimens are summarized in Section [3.1](#).

Each dose of RO7234292 will be administered as a single IT bolus injection of 20 mL.

Administration of the first dose will occur via an IT catheter inserted at baseline and also used for CSF sampling. Administration of the second dose will occur via a lumbar puncture using a needle inserted into the L3/L4 space, although placement at a different level (either in the space above or the space below) is allowed if patient anatomy or clinical judgment dictates.

For details on the lumbar puncture and IT bolus dosing procedure, please refer to the lumbar puncture manual and instructional video. Of note, Investigators will perform a predose neurological examination, including fundoscopy, to rule out increased intracranial pressure prior to performing the lumbar puncture, which is a contraindication to the procedure.

Patients will be discouraged from resting supine after the lumbar puncture procedure and will be encouraged to mobilize immediately by walking around at a minimum and, if feasible, walking briskly.

Patients may receive doses, which have previously been investigated in the Phase I/IIa MAD study (ISIS 443139-CS1) or OLE study (ISIS 443139-CS2), ranging from 30 to

120 mg of RO7234292. The decision to determine which doses will be explored after the initial three dose levels of 120 mg, 60 mg, and 30 mg will be made following review of all relevant safety, tolerability, PK, and biomarker data collected from all previous patients.

The patient's bladder must be completely emptied at the time of study drug administration.

No dosage adjustment from planned treatment is permitted in this study. If a patient misses a dose visit, the Investigator should contact the Medical Monitor to determine appropriate continuation of the patient in the study.

Cases of accidental overdose or medication error, along with any associated adverse events, should be reported as described in Section [5.4.4](#).

Guidelines for treatment interruption or discontinuation for patients who experience adverse events are provided in Section [5.1.3](#).

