4.5.5 Collection of Cerebrospinal Fluid (Lumbar Puncture Procedure)

*Skin (groin area) and nose swabs will be taken during screening to test for Methicillin-resistant *Staphylococcus aureus* (MRSA). If the MRSA screening result is positive, treatment for decolonization (as per local standard procedure) should be administered for 5 days prior to catheter insertion.*

In preparation for the catheter insertion, patients will be required to remove all body piercings, make up, and nail polish and to cleanse the entire body (including hair) with antibacterial soap on Day -2 or Day -1.

Within 72 hours prior to performing each scheduled lumbar puncture or IT catheter insertion, local laboratory analysis of coagulation factors (international normalized ratio [INR], activated partial thromboplastin time [aPTT], prothrombin time [PT]) and platelets must be conducted and the results reviewed. Each lumbar puncture should be performed at approximately the same time at each visit (ideally in the morning between 8:00 a.m. and 12:00 noon or in the early afternoon between 12:00 noon and 3:00 p.m.) to minimize potential diurnal variation of CSF parameters. *A 20 mL sample will be taken at predose after the IT catheter has been inserted. Subsequently, during the CSF sampling period until 48 hours postdose, a maximum 5 mL of CSF fluid will be collected (via the IT catheter) at each timepoint indicated in [Appendix 2](#). In addition, up to 2 mL CSF sample will be collected for daily CSF safety testing, including culture, during the indwelling-catheter period at the timepoints indicated in [Appendix 1](#) and [Appendix 2](#). Upon removal, the catheter tip should be sent for culture.*

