Appendix 1: Schedule of Activities

- u) Plasma PK sampling will be collected as follows: at Day 1 (0 [predose], 1, 2, 4, 6, 8, 12, and 16 hours postdose), Day 2 (24 and 36 hours postdose), Day 3 (48 and 60 hours postdose), Day 4 (72 hours postdose), Day 28 (at a timepoint equivalent to Day 1 predose sample), Day 29 (0 [predose], 1, 2, and 4 hours postdose), Day 30, 43, 71, and 127 (at a timepoint equivalent to Day 29 predose sample), and the follow-up visit (early termination visit if applicable).
- v) Bladder must be completely emptied at the time of study drug administration. Quantitative urine will be collected in the following intervals: 0 to 24 hours, 24 to 48 hours, and 48 to 72 hours following first study drug administration.
- w) Cerebrospinal fluid sampling will be performed from *predose* to (and including) 48 hours postdose via the IT catheter, at all other visits CSF sampling will be done by single lumbar puncture. Pharmacokinetic CSF sampling will be collected as follows: at Day 1 (0 [predose], 2, 4, 8, 12, and 16 hours postdose), Day 2 (24 and 36 hours postdose), Day 3 (48 hours), Day 29 (predose), Day 43, 71, and 127, and the follow-up visit (early termination visit if applicable). Sampling for CSF biomarkers will be collected as follows: Day 1 (0 [predose], 4, 8, 12, and 16 hours postdose), Day 2 (24 and 36 hours postdose), Day 3 (48 hours postdose), Day 29 (predose), Day 43, 71, and 127, and the follow-up visit (early termination visit if applicable). *In addition, up to 2 mL CSF sample will be collected for daily CSF safety testing, including culture, during the indwelling-catheter period.*
- x) Sampling for plasma biomarkers will be collected as follows: at Day -1 (-24, -20, -16, -12, and -8 hours), Day 1 (0 [predose], 1, 2, 4, 6, 8, 12, and 16 hours postdose), Day 2 (24 and 36 hours postdose), Day 3 (48 and 60 hours postdose), Day 4 (72 hours postdose), Day 29 (predose), Day 43, 71, and 127, and the follow-up visit (early termination visit if applicable).
- y) Admission to the clinical unit may occur either on the evening/afternoon of Day -2 or the morning of Day -1. *Assessments for Day -2 should be conducted on Day -2, but it is not mandatory for the patient to remain at the clinic overnight on Day -2 if it is more convenient to stay at a hotel or return home.*

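### The time-matched baseline in SAP 4.2 is not available for CSF under the current schedule, and the early CSF mHTT change cannot be separated from the 20 mL fluid exchange (and, at most early times, from time of day)

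*SAP*

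**What the plan says.** Protocol 2.1.1 lists "Change from baseline of mHTT concentrations in CSF" as a primary endpoint. SAP 4.2 sets one rule for all assessments, "baseline will be defined as the last non-missing measure prior to the first dose administration", and then adds the option "For fluid biomarkers, if appropriate time-matched baseline may also be considered to assess diurnal effects". It does not say which fluids this covers or what would make it appropriate.

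For the schedule, protocol Appendix 1, footnote w, has "Sampling for CSF biomarkers will be collected as follows: Day 1 (0 [predose], 4, 8, 12, and 16 hours postdose", followed by 24, 36 and 48 h. No CSF is scheduled before 0 h. The CSF PK series adds one more draw, at 2 h: "Pharmacokinetic CSF sampling will be collected as follows: at Day 1 (0 [predose], 2, 4, 8, 12, and 16 hours postdose". Footnote x gives plasma biomarkers five Day -1 samples, at -24, -20, -16, -12 and -8 h.

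For volumes, protocol 4.5.5 states "A 20 mL sample will be taken at predose after the IT catheter has been inserted". Up to 5 mL follows at each later catheter time, plus up to 2 mL a day for safety tests. Protocol 4.3.2 states "Each dose of RO7234292 will be administered as a single IT bolus injection of 20 mL", and 5.1.3.1 fixes that volume for every participant.

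Protocol 4.5.5 and Appendix 1, footnote aa, ask for lumbar punctures at a similar clock time because CSF parameters may vary over the day. Footnote aa exempts the sampling around the first dose.

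SAP 4.8.1 and Table 5 tabulate and plot mHTT and CSF NfL as absolute value, change and percentage change at every available time. SAP 4.9 models mHTT with nonlinear mixed effects and leaves the details to a separate document. Neither the protocol nor the SAP mentions dilution, withdrawn volume or a time-of-day term in the analysis. The study is open-label, with no vehicle or undosed group.

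**The concern.** The catheter series is there to give a finer time course than earlier studies had. Between the 0 h sample and the early postdose samples, however, three things change together: drug is present, CSF has been exchanged for injectate, and, at most times, the clock hour differs. With no vehicle group and no predose CSF series, the planned tables and plots cannot separate them.

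The order of events makes this matter. Protocol 1.2 describes a drug that reduces synthesis of the protein, so mHTT already present has to clear before the concentration falls by that route. Dilution acts at once. The earliest samples are therefore where a fall unrelated to the drug is easiest to read as onset of effect.

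At stake are the absolute early change from baseline and the onset and turnover parameters of the PK/PD model. Protocol 3.3.1 says the time course of effect may inform a different regimen.

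**Working it through.** The documents give no dilution figure or diurnal amplitude, so there is no planned number to reproduce. The one place where CSF volume is used is the safety margin in protocol 3.3.1, and it is arithmetically consistent: 150/15 = 10; 35 × 10 = 350 mg; 350/120 = 2.9, stated as 3-fold. That section gives 150 mL as a lower bound for human CSF volume.

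**Step 1, clock matching.** A postdose time *t* is matched if a predose sample *s* exists with (*t* − *s*) a multiple of 24 h.

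| CSF biomarker time (h) | Predose CSF match (h) | Predose plasma match (h) |
|---|---|---|
| 4 | none | -20 |
| 8 | none | -16 |
| 12 | none | -12 |
| 16 | none | -8 |
| 24 | 0 | -24, 0 |
| 36 | none | -12 |
| 48 | 0 | -24, 0 |

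Five of the seven CSF times are unmatched. Plasma has a match at all seven. For 24 and 48 h the default baseline is already the CSF match.

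**Step 2, immediate effect of the exchange.** Assume a well-mixed volume *V* and injectate without mHTT. The fall is 20/*V*: 20/150 = 13.3%, 20/200 = 10%, 20/250 = 8%.

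**Step 3, fading.** The documents give no recovery rate, so the half-life *h* is assumed. The residual shift is −13.3 × 0.5^(*t*/*h*) at *V* = 150 mL, in percentage points of baseline:

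| Assumed half-life | 4 h | 16 h | 24 h | 36 h | 48 h |
|---|---|---|---|---|---|
| 3 h | -5.3 | -0.3 | -0.1 | 0.0 | 0.0 |
| 6 h | -8.4 | -2.1 | -0.8 | -0.2 | -0.1 |
| 12 h | -10.6 | -5.3 | -3.3 | -1.7 | -0.8 |
| 24 h | -11.9 | -8.4 | -6.7 | -4.7 | -3.3 |

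At *V* = 250 mL the 4 h range is -3.2 to -7.1 and the 48 h range 0.0 to -2.0.

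**Step 4, serial withdrawal.** Up to 20 + 7 × 5 + 2 × 2 = 59 mL is taken by 36 h and 20 + 8 × 5 + 3 × 2 = 66 mL by 48 h (39% and 44% of 150 mL), or 2 mL less if the Day 1 safety sample is part of the 20 mL. Removing well-mixed fluid does not itself change a concentration; what matters is what replaces it. If every withdrawal were replaced by mHTT-free fluid, an upper bound, the combined shift over the same half-lives at 150 mL would be -7.2 to -14.6 points at 4 h, -0.3 to -13.9 at 36 h and -0.2 to -11.9 at 48 h.

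**Step 5, later samples.** Day 29 is 28 days after the first exchange, and Day 43 is nominally 14 days after the second. Even with a 24 h half-life, 13.3 × 0.5^14 is below 0.001 points. These are single samples taken at about the same clock time.

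**The case against.** Several objections are sound and limit the point.

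- *The SAP does not promise a time-matched CSF baseline.* The clause is permissive and covers fluid biomarkers generally, and it works for plasma NfL. A reader might infer that a planned analysis has become impossible. The text supports only that an optional clause needs its scope stated.
- *Some patients may have earlier CSF.* The summary of changes records that the catheter used to be inserted 24 h before dosing, and protocol 5.1.1.4 describes catheters in place for 4 days among the first 6 patients. Dose follows enrolment order (SAP 2), however. If groups filled in order, those six would be four at 120 mg and two at 60 mg, so a matched baseline from them alone would be tied to dose.
- *The size is assumed.* The half-life has no source in the documents, and 150 mL is a lower bound. The shift at later catheter times could be close to zero.
- *The modelling document is not available to us.* It may already include these terms. One cannot say that the model is misspecified, only that neither document says the terms will be there.
- *The planned outputs help somewhat.* An early fall common to all doses, and seen in both mHTT and NfL, would be visible in the profiles. Nothing in the SAP tells the reader how to interpret it.

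It is also tempting to set 13% against the predicted "percentage change from baseline of CSF mHTT of -24%, -27%, -29%, and -30%, respectively" and conclude that half the drug effect could be artefact. The documents do not support that. Those predictions apply 29 days after the second dose, about Day 58, and no prediction is given for the first 48 h.

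**Conclusion.** The point stands in a limited form. Under the current schedule a time-matched baseline cannot be formed for CSF mHTT or CSF NfL at 4, 8, 12, 16 and 36 h. At 24 and 48 h the clock time matches, so only exchange and withdrawal are in question there.

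The exchange can lower early mHTT without drug action by about 13% at once (150 mL, well mixed) or 10% (200 mL). For assumed half-lives of 3 to 24 h at 150 mL, that is about -5 to -12 points at 4 h and 0 to about -3 at 48 h. Poor mixing in the lumbar space could make the earliest values larger, and withdrawals could add to the shift up to the bound in step 4. The time-of-day component cannot be sized from the documents.

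A reader might infer that the dose comparison or the trough reduction is compromised. It is not: the injected volume is the same at every dose level, which largely protects contrasts between doses, and samples from Day 29 on are little affected. The exposure is to the absolute early change and to modelled onset and turnover. As written, the plan would report any exchange-related fall as mHTT change from baseline, without comment.

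**What to change.** 1. **SAP 4.2.** Limit the time-matched baseline to plasma biomarkers. If any patient enrolled under an earlier protocol version has Day -1 CSF, show it descriptively only and give the reason: dose follows enrolment order.
2. **SAP 4.8.1 and Table 5.** Keep every early point. Footnote 4, 8, 12, 16 and 36 h as not separable from CSF exchange and time of day, and 24 h as possibly affected by exchange only. Base statements on the size of the drug effect on 48 h and later; of the catheter samples, 48 h is clock-matched and furthest from the exchange.
3. **SAP 4.9.** Fit the mHTT model with the 20 mL exchange as a known event and a CSF turnover term, adding withdrawals at recorded volume or, failing that, nominal volume. Do this at least as a sensitivity analysis, and report whether the onset and turnover estimates change.

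Expressing mHTT relative to NfL in the same sample is not recommended as a correction, because NfL is itself an exploratory response marker (protocol 2.3).

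No new samples are needed. The cost is SAP wording, some extra modelling, and less weight on the early points that the catheter was placed to obtain.
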